11.4 Secondary and exploratory analyses

Secondary analyses

The proportion of patients who have clinical benefit will be calculated and an estimate of 90% confidence interval will be provided.

The frequency and maximum severity of acute adverse events will be tabulated graded by CTCAE v5.0.

Kaplan-Meier median estimates and graphs will be used to describe PFS and OS survival functions.

Exploratory analyses

Summary statistics (and graphs where it is appropriate) will be done for exploratory biomarker endpoints.

Appropriate methods will be implemented to explore the associations of biomarkers with the response and clinical benefit, e.g., Spearman's correlation coefficient for interval/ordinal type of

biomarker measurements with response or clinical benefit, chis-squared test for nominal type of biomarker measurements with response or clinical benefit.

The purpose of exploratory objective is to explore and possibly generate hypotheses for future study. Therefore there will be no adjustment for multiple tests.

11.5 Only those patients who are deemed "ineligible" or who receive no therapy will be eliminated from the analysis. All patients who receive any therapy will be evaluated for both treatment efficacy and toxicity. While on occasion, circumstances may prevent the determination of treatment efficacy, such patients will be included in the analysis and labeled as "unknown". This category will be listed and be reflected in the calculation of the response rate.

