8.1.1 Definitions

Evaluable for toxicity. All patients will be evaluable for toxicity from the time of their first treatment with ribociclib and letrozole

Evaluable for objective response. Only those patients who have measurable disease present at baseline, have received at least one cycle of therapy, and have had their disease re-evaluated will be considered evaluable for response. These patients will have their response classified according to the definitions stated below. (Note: Patients who exhibit objective disease progression prior to the end of cycle 1 will also be considered evaluable.)

Evaluable Non-Target Disease Response. Patients who have lesions present at baseline that are evaluable but do not meet the definitions of measurable disease, have received at least one cycle of therapy, and have had their disease re-evaluated will be considered evaluable for non-target disease. The response assessment is based on the presence, absence, or unequivocal progression of the lesions.

Disease Parameters

Measurable disease. Measurable lesions are defined as those that can be accurately measured in at least one dimension (longest diameter to be recorded) as \geq 20 mm by chest x-ray, as \geq 10 mm with CT scan, or \geq 10 mm with calipers by clinical exam. All tumor measurements must be recorded in millimeters (or decimal fractions of centimeters).

Note: Tumor lesions that are situated in a previously irradiated area might or might not be considered measurable. If the investigator thinks it appropriate to include them, the conditions under which such lesions should be considered must be defined in the protocol.

Malignant lymph nodes. To be considered pathologically enlarged and measurable, a lymph node must be \geq 15 mm in short axis when assessed by CT scan (CT scan slice thickness recommended to be no greater than 5 mm). At baseline and in follow-up, only the short axis will be measured and followed.

Non-measurable disease. All other lesions (or sites of disease), including small lesions (longest diameter <10 mm or pathological lymph nodes with ≥ 10 to <15 mm short axis), are considered non-measurable disease. Bone lesions, leptomeningeal disease, ascites, pleural/pericardial effusions, lymphangitis cutis/pulmonitis, inflammatory breast disease, and abdominal masses (not followed by CT or MRI), are considered as non-measurable.

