8.1.6 Reporting of tumor response

All patients included in the study must be assessed for response to treatment, even if there is a major protocol deviation or if they are ineligible, or not followed/re-evaluated. Each patient will be assigned one of the following categories: complete response, partial response, stable disease, progressive disease, early death from malignant disease, early death from toxicity, early death from other cause or unknown (not assessable, insufficient data).

Early death is defined as any death occurring before the first per protocol time point of tumor reevaluation. The responsible investigator will decide if the cause of death is malignant disease, toxicity, or other cause.

Patients for whom response is not confirmed will be classified as "unknown" unless they meet the criteria for stable disease (or the criteria for partial response in case of an unconfirmed complete response). Patients' response will also be classified as "unknown" if insufficient data were collected to allow evaluation per these criteria. See table above for further detail.

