We will target an accrual of 23 eligible and evaluable patients in the first stage of this study, but in practice permit accrual to range from 19 to 26 patients due to administrative coordination. If there are more than 2 out of 19-25, or 3 out of 26 patients responding (complete or partial response) and medical judgment indicates, accrual to the second stage of the trial will be initiated. Otherwise, the study will be stopped and the treatment regimen will be classified as clinically uninteresting. If the study advances to the second stage, then an overall study accrual of 48 eligible and evaluable patients will be targeted, but permitted to range from 44 to 51 patients for administrative reasons. If more than 6 out of 44-45 patients respond or 7 out of 46-51 patients respond then the regimen will be considered worthy for additional investigation.

Under the assumed accrual ranges of 19 to 26 (stage 1) and 44 to 51 (cumulatively after stage 2), if the true probability of response is 10% (H0), then this study has a 64% probability of early termination and a probability of 10% of incorrectly declaring the study regimen interesting; if the true probability of tumor response is 25%, then the study has a 90% chance of correctly classifying the study regimen as being interesting.

The following table summarizes the accrual and decision guideline.

Stage of	Targeted	Limits of Actual	Max Number of Responses to
Accrual	Cumulative Accrual	Accrual	Reject Study Regimen
1	23	19-26	2/(19-25), 3/26
2	48	44-51	6/(44-45), 7/(46-51)

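### Section 11.5 removes treated patients deemed ineligible from toxicity as well as response, and nothing requires that ruling to be made before response is known

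*Combined protocol and SAP*

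**What the plan says.** Section 11.5 sets the analysis population in consecutive sentences. The first is "Only those patients who are deemed 'ineligible' or who receive no therapy will be eliminated from the analysis". The second is "All patients who receive any therapy will be evaluated for both treatment efficacy and toxicity". The section then keeps patients whose response could not be determined, as a category of unknown: "This category will be listed and be reflected in the calculation of the response rate".

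Three other places bear on the same patients:

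- Section 8.1.1 (Definitions), on toxicity: "All patients will be evaluable for toxicity from the time of their first treatment with ribociclib and letrozole". It sets no eligibility condition.
- Section 8.1.6 (Reporting of tumor response): all patients in the study "must be assessed for response to treatment, even if there is a major protocol deviation or if they are ineligible", and each is given a response category.
- Sections 11.0 and 11.3 set both accrual targets (23, then 48 cumulatively) in eligible and evaluable patients. The final rule is "If more than 6 out of 44-45 patients respond or 7 out of 46-51 patients respond", and the summary table in 11.3 confirms that 7 of 46-51 is a rejection. At stage 1, 3 responders of 19-25 may continue and 3 of 26 stops.

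**The concern.** Two issues follow.

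**Toxicity.** The first sentence of 11.5 speaks of the analysis without limiting it to response, and the second names efficacy and toxicity together. An analyst following the first sentence would take a treated patient's adverse events out of the tables because of an eligibility finding. An analyst following 8.1.1 would keep them. The first course undercounts harm among people who took the drugs.

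**Response.** The trial is open-label and single-arm, so each patient's response is known at the site. The plan puts no limit on when a patient may be deemed ineligible, on what evidence, or by whom. Because the boundaries change with the number analysed, a late ruling on a non-responder can alter the denominator and, near a step, the conclusion.

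**Working it through.** **1. Setting the texts side by side, for a treated patient deemed ineligible**

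| Place | Toxicity | Response |
|---|---|---|
| 11.5, first sentence | out | out |
| 11.5, second sentence (literal) | in | in |
| 8.1.1, toxicity definition | in | not addressed |
| 8.1.6 | not addressed | assessed and categorised |
| 11.0 and 11.3 | not addressed | not counted towards the targets |

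If the second sentence of 11.5 is read as covering only those who remain after the first, the clash inside 11.5 disappears. The clash with 8.1.1 on toxicity does not.

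**2. Reproducing the design figures**

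Inputs from Section 11.3: null response rate 0.10 and alternative 0.25; n1 = 19-26 with maximum responses to stop r1 = 2 (19-25) or 3 (26); cumulative n2 = 44-51 with maximum responses to reject r2 = 6 (44-45) or 7 (46-51).

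With X ~ Bin(n1, π) and Y ~ Bin(n2 − n1, π):

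- P(stop early) = P(X ≤ r1)
- P(declare) = Σ over x > r1 of P(X = x) · P(Y ≥ r2 + 1 − x)

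Averaged with equal weight over the 8 × 8 = 64 accrual pairs:

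| Quantity | Recomputed | Stated |
|---|---|---|
| Early termination, π = 0.10 | 63.6% | 64% |
| Type I error | 9.9% | 10% |
| Power, π = 0.25 | 90.0% | 90% |

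The plan's figures reproduce.

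**3. Where removing one non-responder changes a verdict**

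Comparing x of n with x of n − 1 over the permitted ranges gives exactly two points:

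- Final: 7/46 (15.2%) rejects; 7/45 (15.6%) succeeds.
- Stage 1: 3/26 (11.5%) stops; 3/25 (12.0%) may continue.

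With 7 responders, the number of removals needed to reach 45 is n2 − 45: one at 46, two at 47, three at the target of 48. At the stage 1 target of 23, no single removal matters.

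**4. Worst-case effect on type I error**

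Suppose that whenever the trial passes stage 1 and ends with exactly 7 responders, enough non-responders are removed to reach 45. The added false-positive probability at a given n2 is P(pass stage 1 and total = 7). At π = 0.10, averaged over n1, this is 6.47% at n2 = 46, 6.65% at 47 and 6.82% at 48. Each n2 carries weight 1/8, so from a base of 9.88%:

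- one removal: 9.88 + 6.47/8 = 10.7%
- up to two: 9.88 + (6.47 + 6.65)/8 = 11.5%
- up to three: 9.88 + (6.47 + 6.65 + 6.82)/8 = 12.4%

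If the single removal is also used at 3/26, the one-removal figure is 10.9%.

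**The case against.** The strongest reply is that excluding ineligible patients from the response decision is the stated design. Sections 11.0 and 11.3 count eligible and evaluable patients, the boundaries are indexed to that number, and the error rates are correctly calculated for it. That stands.

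There are also safeguards. Central pathology review is prospective (Sections 6.1 and 7.2), registration requires all other eligibility criteria to be met, and unknown responses stay in the denominator, which closes a commoner route for losing non-responders. These narrow the opening. They do not close it, because no central check is described for the laboratory, ECG, prior-therapy and measurable-disease criteria. The documents give no rate of late ineligibility, and late rulings are a possibility the text leaves open, not something it foresees.

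Four stronger readings are tempting and not supported:

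- *Section 8.1.6 contradicts 11.5 on the denominator.* It governs assessment and reporting. A patient can be assessed, categorised and still left out of the primary count.
- *One removal can overturn the result at the planned size.* It cannot at 23 or 48.
- *Type I error rises to about 15%.* With n1 = 23 and n2 fixed at 46, 47 or 48, outcome-driven removal takes it from 7.6/8.3/9.0% to 14.6/15.5/16.4%. Those figures condition on n2 and on the needed removals being found every time. The plan controls the average over accrual pairs, and the design already has 13.7% at n1 = 23, n2 = 45 with nobody removed.
- *A patient with a dose-limiting toxicity could be dropped from the safety lead-in and replaced.* Section 4.6 replaces only patients without a DLT who do not complete cycle 1, and 11.3 counts as evaluable anyone who had a DLT. Neither sets an eligibility condition.

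**Conclusion.** The point holds in two parts. The conflict between 11.5 and 8.1.1 on toxicity is plain in the text and survives the charitable reading of 11.5; it needs no assumption. On response, the exclusion itself is consistent with the design. The gap is that nothing requires it to be settled from baseline data before response is known.

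The size of the response part is modest: at worst, average type I error of 10.7% to 12.4% for one to three removals, against 9.9% as designed. This assumes equal weight on the 64 accrual pairs, removal driven by outcome, and enough removable non-responders each time the count is exactly 7. Removal unrelated to outcome is not the mechanism calculated here. Severity: should-fix.

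**What to change.** Rewrite Section 11.5 so that:

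1. every patient who takes any dose is in the toxicity tables, as 8.1.1 already says;
2. ineligibility for the response analysis is decided only from pre-treatment records, without knowledge of response and before response data are tabulated, and the resulting list fixes n for the 11.3 boundaries;
3. the response rate in all treated patients is reported alongside as a sensitivity result.

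A cross-reference from 8.1.6 would make clear that assessing and categorising an ineligible patient does not by itself place her in the primary denominator.

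The cost is a few sentences and one table row. No boundary or sample size changes, and the 64%, 10% and 90% figures stand. The one drawback is that any wrongly enrolled patient slightly dilutes the all-treated rate.

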APPENDIX A: PERFORMANCE STATUS SCALES

PERFORMANCE STATUS CRITERIA						
ECOG	(Zubrod)	Karnof	sky	Lansky	/	
Score	Description	Score	Description	Score	Description	
	Fully active, able to carry on all pre-disease	100	Normal, no complaints, no evidence of disease.	100	Fully active, normal.	
0	performance without restriction.	90	Able to carry on normal activity, minor signs or symptoms of disease.	90	Minor restrictions in physically strenuous activity.	
	Restricted in physically strenuous activity but	80	Normal activity with effort, some signs or symptoms of disease.	80	Active, but tires more quickly.	
1	ambulatory and able to carry out work of a light or sedentary nature, e.g., light housework, office work.	70	Cares for self, unable to carry on normal activity or do active work.	70	Both greater restriction of, and less time spent in, play activity.	
	Ambulatory and capable of all selfcare but unable	60	Requires occasional assistance, but is able to care for most of his/her needs.	60	Up and around, but minimal active play; keeps busy with quieter activities.	
2	to carry out any work activities. Up and about more than 50% of waking hours.	activities. Up and about more than 50% of	50	Requires considerable assistance and frequent medical care.	50	Gets dressed, but lies around much of the day; no active play; able to participate in all quiet play and activities.
3	Capable of only limited selfcare, confined to bed	40	Disabled, requires special care and assistance.	40	Mostly in bed, participates in quiet activities.	
3	or chair more than 50% of waking hours.	30	Severely disabled, hospitalization indicated. Death not imminent.	30	In bed, needs assistance even for quiet play.	
4	Completely disabled. Cannot carry on any	20	Very sick, hospitalization indicated. Death not imminent.	20	Often sleeping, play entirely limited to very passive activities.	
4	selfcare. Totally confined to a bed or chair.	10	Moribund, fatal processes progressing rapidly.	10	No play, does not get out of bed.	
5	Dead	0	Dead	0	Dead	

As published in Am J Clin Oncol: Oken MM, Creech RH, Tormey DC, Horton J, Davis TE, McFadden ET, Carbone PP. Toxicity and Response Criteria of the Eastern Cooperative Oncology Group. Am J Clin Oncol 1982;5:649-655. The Eastern Cooperative Oncology Group, [name], Group Chair.

APPENDIX B: NYHA CLASSIFICATION OF HEART DISEASE

New York Heart Association (NYHA) classification of heart disease

Table 1: NYHA Classification of Heart Disease

NYHA Class	Symptoms
1	No symptoms and no limitation in ordinary physical activity, e.g. shortness of breath when walking, climbing stairs etc.
II	Mild symptoms (mild shortness of breath and/or angina) and slight limitation during ordinary activity.
III	Marked limitation in activity due to symptoms, even during less-than- ordinary activity, e.g. walking short distances (20–100 m). Comfortable only at rest.
IV	Severe limitations. Experiences symptoms even while at rest . Mostly bedbound patients.

APPENDIX C: PROHIBITED MEDICATIONS DURING STUDY DRUG TREATMENT

Table 1. List of prohibited medications during study drug treatment

Drug Name
Atazanavir/ritonavir, boceprevir, clarithromycin, cobicistat, conivaptan, danoprevir/ritonavir, darunavir/ritonavir, elvitegravir/ritonavir, grapefruit juice, idelalisib, indinavir, indinavir/ritonavir, itraconazole, ketoconazole, lopinavir/ritonavir, mibefradil, nefazodone, nelfinavir,ombitasvir/paritaprevir/dasabuvir/ritonavir (VIEKIRA PAK), posaconazole, ritonavir, saquinavir/ritonavir, telaprevir, telithromycin, tipranavir/ritonavir, troleandomycinvoriconazole
Apalutamide, carbamazepine ³ , enzalutamide, lumacaftor, mitotane, phenobarbital, phenytoin ³ , rifabutin, rifampin (rifampicin) ³ , St. John's wort (hypericum perforatum) ^{2,3}
Alfentanil, astemizole, cisapride, cyclosporine, diergotamine (dihydroergotamine), ergotamine, fentanyl, pimozide, quinidine, sirolimus, tacrolimus
Amiodarone, anagrelide, arsenic trioxide, astemizole, azithromycin, chloroquine, chlorpromazine, cilostazol, ciprofloxacin, cisapride, citalopram, clarithromycin, disopyramide, dofetilide, domperidone, donepezil, dronedarone, droperidol, erythromycin, escitalopram, flecainide, fluconazole, gatifloxacine, grepafloxacin, halofantrine, haloperidol, ibutilide, levofloxacin, levomepromazine, levosulpiride, methadone, moxifloxacin, ondansetron, oxaliplatin, papaverine HCl (intracoronary), pentamidine, pimozide, procainamide, propofol, quinidine, roxithromycin, sevoflurane, sotalol, sulpiride, sultopride, terlipressin, terodiline, thioridazine, vandetanib
Herbal preparations/medications or dietary supplements known as strong inducers or inhibitors of CYP3A4/5 or those with a known risk of QT prolongation are prohibited throughout the study. These herbal medications include, but are not limited to: St. John's wort, Kava, ephedra (ma huang), gingko biloba, dehydroepiandrosterone (DHEA), yohimbe, saw palmetto, and ginseng. Patients should stop using these herbal medications or dietary supplements 7 days prior to first dose of study drug.
Other investigational therapies must not be used while the patient is on the study. Anticancer therapy (chemotherapy, all SERMS (including raloxifene), biologic or radiation therapy, and surgery) other than the study treatments must not be given to patients while the patient is on the study medication. If such agents are required

¹ NTI = narrow therapeutic index drugs whose exposure-response indicates that increases in their exposure levels by the concomitant use of potent inhibitors may lead to serious safety concerns (e.g., Torsades de Pointes) or drugs which have <2-fold difference in the minimum toxic concentrations and minimum effective concentrations in the blood.

As far as possible, avoid co-administration of QT prolonging drugs or any other drugs with the potential to increase the risk of drug-related QT prolongation (e.g., via a potential DDI that increases the exposure of ribociclib or the exposure of the QT prolonging drug). A definitive list of drugs with a known risk, possible risk, or conditional risk of QT prolongation and/or Torsades de Pointes (TdP) is available online at qtdrugs.org.

Source: Novartis PK Sciences Memorandum: Drug-Drug Interactions (DDI) and Co-medication Considerations for Novartis Clinical Trials (January 2018), which is compiled from Indiana University "Clinically Relevant" Flockhart Table™, University of Washington Drug Interaction Database, and FDA Drug Development and Drug Interactions: Table of Substrates, Inhibitors and Inducers.

² Herbal product

³ P-gp inducer

⁴ The list provided is as of December 2019. Check https www crediblemeds.org/healthcare-providers/drug-list for the most updated list.

Table 2. List of medications to be used with caution during study drug treatment

Category	Drug Name
Moderate CYP3A4/5 inhibitors	Aprepitant, amprenavir, asafoetida resin (Ferula asafoetida) cimetidine, crizotinib, diltiazem, faldaprevir, imatinib, isavuconazole, netupitant, nilotinib, tofisopam, Schisandra sphenanthera (nan wu wei zi), verapamil
Moderate CYP3A4/5 inducers	Bosentan, dabrafenib, efavirenz, etravirine, genistein,lopinavir ⁵ , modafinil, nafcillin,telotristat
Sensitive CYP3A4/5 substrates ¹	Alpha-dihydroergocryptine, aprepitant, atorvastatin, avanafil, bosutinib,brotizolam, budesonide, buspirone, cannabinoids ⁶ , cannabidiol ⁶ , cobimetinib, darifenacin, dasatininb, ebastine, eletriptan, eplerenone, everolimus, felodipine, fluticasone, grazoprevir, ibrutnib, isavuconazole, ivabradine, ivacaftor, , levomethadyl (LAAM), lomitapide, lovastatin, lumefantrine, lurasidone, maraviroc, midazolam, midostaurin, naloxegol, neratinib, nisoldipine, perospirone, quetiapine, ridaforolimus, sildenafil, simeprevir, simvastatin, ticagrelor, tilidine, tolvaptan, triazolam, ulipristal, vardenafil, venetoclax, vicriviroc, voclosporin
BSEP inhibitors	Alectinib, atorvastatin, bromocriptine, candesartan, clobetasol, clofaziminie, dabigatran, dipyridamole, glyburide, grazoprevir, ledipasvir, mifepristone,pioglitazone, reserpine,rifamycin, simeprevir, telmisartan,timcodar, troglitazone, valinomycin, velpatasvir
Medications that carry a possible risk for QT prolongation ²	Alfuzosin, apomorphine, aripiprazole, artenimol+piperaquine, asenapine, atomoxetine, bedaquiline, bendamustine, bortezomib, bosutinib, buprenorphine, cabozantinib, capecitabine, ceritinib, clomipramine, crizotinib, clozapine, cyamemazine (cyamepromazine), dabrafenib, dasatinib, degarilix, delamanid, desipramine, dexmedetomidine, dolasetron, efavirenz, eliglustat, epirubicin, eribulin mesylate, ezogabine(retigabine), famotidine, felbamate, fingolimod, flupentixol, gemifloxacin, granisetron, hydrocodone-ER, iloperidone, imipramine (melipramine), isradipine, ketanserin, lapatinib, lenvatinib, leuprolide, lithium, melperone, midostaurin, mifepristone, mirabegron, mirtazapine, moexipril/HCTZ, necitumumab, nicardipine, nilotinib, norfloxacin, nortriptyline, nusinersen, ofloxacin, osimertinib, oxytocin, paliperidone, palonosetron, panabinostat, pasireotide, pazopanib, perflutren lipid microspheres, perphenazine, pilsicainide, pimavanserin, pipamperone, promethazine, prothipendyl, rilpivirine, risperidone, romidepsin, sertindole, sorafenib, sunitinib, tamoxifen, tipiracil/trifluridine, tizanidine, tolterodine, toremifene,trimipramine, tropisetron, vardenafil, vemurafenib, venlafaxine, vorinostat, ziprasidone
MATE1/2 substrates ³	Acyclovir, cephalexin, cimetidine, fexofenadine, ganciclovir, glycopyrronium, metformin, pindolol, plisicainide, ranitidine, topotecan, varenicline
OCT1/2 substrates ⁴	Amantadine, 6-beta-hydroxycortisol, carboplatin, cisplatin, cephalexin, cephradine, ipratropium, lamivudine, linagliptin, metformin, oxali platin, oxybutynin, phenformin, picoplatin, pilsicainide, pindolol, , ranitidine, sorafenib, tropisetron, trospium, umeclidinium,, , and zidovudine
BCRP substrates	Daunorubicin, dolutegravir, doxorubicin, hematoporphyrin, imatinib, methotrexate, mitoxantrone, pitavastatin, rosuvastatin, irinotecan, ethinyl estradiol, simvastatin, sulfasalazine, sofosbuvir, tenofovir, topotecan, venetoclax

¹ Sensitive substrates: Drugs whose plasma AUC values have been shown to increase 5-fold or higher when co-administered with a potent inhibitor.² The list provided is as of January 2018. Check https www crediblemeds.org/healthcare-providers/drug-list for the most updated list.

³ MATE1 and MATE2 share considerable substrate specificity.

⁴ OCT1 and OCT2 share considerable substrate specificity.

⁵ Lopinavir and atazanavir is prohibited when combined with ritonavir (see Table 14-1)

⁶ Based data that, exposure of cannabidiol (CBD), tetrahydrocannabinol (THC), 11-hydroxy THC, increased by ~2-3 folds when co-administered with ketoconazole (CYP3A4 inhibitor); Stott et al, Springerplus. 2013; 2: 236

Category	Drug Name

Source: Novartis PK Sciences Memorandum: Drug-Drug Interactions (DDI) and Co-medication Considerations for Novartis Clinical Trials (January 2018), which is compiled from Indiana University "Clinically Relevant" Flockhart Table™, University of Washington Drug Interaction Database, and FDA Drug Development and Drug Interactions: Table of Substrates, Inhibitors and Inducers.

